8.3.1 AE Follow up

All AEs occurring during the study are to be followed up in accordance with good medical practice until they are resolved, stabilized or judged no longer clinically significant or, if a chronic condition, until fully characterized. Any AEs that are considered drug-related (possibly related, definitely related) must be followed for 30 days, or to resolution, or until no improvement is expected, whichever occurs first.

8.3.2 Overdose

No information on treatment of overdose of Ampion is currently available. In the case of overdose the patient should be followed as for an AE and appropriate supportive medical treatment instigated.

8.4 Serious Adverse Event Reporting

8.4.1 Reporting Requirements

Unexpected serious suspected adverse reactions are subject to expedited reporting to FDA. All SAEs must be entered into the eCRF within 24 hours of first knowledge of the event by study personnel. The investigator must provide his/her assessment of the relationship to study drug at the time of the initial report. The entry of an SAE into the eCRF triggers an automatic alert to the clinical research organization (CRO) safety team. The following information must be reported:

- Protocol number
- Site and/or Investigator number
- Patient number
- Demographic data
- Brief description of the event
- Onset date and time
- Resolution date and time, if the event resolved
- Current status, if event not yet resolved
- Any concomitant treatment and medication
- Investigator's assessment of whether the SAE was related to Investigative product or not.

The CRO Safety Associate will contact the site for clarification of data entered onto the eCRF, or to obtain missing information. In the event of questions regarding SAE reporting, the site may contact the appropriate individual as in [Section 8.4.2](#).

8.4.2 SAE Contact Information

Ampio Pharmaceuticals Inc, or their designee CRO, is responsible for submitting reports of AEs associated with the use of the drug that are both serious and unexpected to FDA according to 21 CFR 312.32 and the final guidance (2012). All investigators participating in ongoing clinical studies with the study medication will receive copies of these reports for prompt submission to their Institutional Review Board (IRB) or Ethics committee (EC).

9 STATISTICAL METHODS

9.1 General Considerations

This section describes the rules and conventions to be used in the presentation and analysis of the data. The details of all these analyses will be presented in the Statistical Analysis Plan.

This trial is designed for approximately 200 patients across two treatment arms (active or control), with a 100 subjects per arm, randomized 1:1 using a random allocation sequence equally stratified by COVID-19 disease severity.

The number of participants is selected based on the effects observed for the primary endpoint, need for mechanical ventilation or death prior to day 28. A study recently reported in Lancet Respiratory Medicine with 243 hospitalized patients receiving the placebo for COVID-19 found 22% did not achieve day 28 ventilation-free survival (Lancet Respir Med 2021; [https://doi.org/10.1016/S2213-2600\(21\)00494-X](https://doi.org/10.1016/S2213-2600(21)00494-X)). In the AP-014 study, a lower rate (8%) was observed for subjects receiving inhaled Ampion. Assuming the same proportions (8% for Ampion and 22% for control) by Day 28, with 100 subjects per group, a two-sided 5% significance level, and using a z-test with unpooled variances, then under binomial enumeration the power to detect this difference is about 81.3%.

9.2 Analysis Populations

9.2.1 Safety Analysis Population:

The safety analysis population is defined as all patients who are randomized. Participants will be analyzed as treated.

9.2.2 Intent-to-treat Population:

The intent-to-treat (ITT) analysis population is defined as all randomized patients. All efficacy analyses will be performed in the ITT population. Patients will be analyzed as randomized.

9.2.3 Interim Analysis

This trial is designed to enroll up to approximately 200 subjects, randomized to active or control, following an equal allocation to treatment arms. An interim analysis of the data is planned after 30 subjects (n=15 subjects per arm) to evaluate the relative effect. At the interim analysis, the sample size may be re-estimated to include additional subjects to attain adequate power up to a 200 total subjects. This will be conducted at an alpha level of 0.001 and thus the overall alpha level for the final test will be performed at $\alpha=0.047$ instead of $\alpha=0.05$. The sponsor also reserves the right to alter the final sample size if the assumptions of the death rates are not satisfied at this interim analysis.

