1 PROTOCOL SUMMARY

1.1 Protocol Synopsis

Sponsor: Ampio Pharmaceuticals, Inc.	Investigational Product: Ampion™						
Title of Study: A Randomized, Double-Blinded, Placebo-Controlled Phase II Study to Evaluate the Safety and Efficacy of Intravenous Ampion in Adult COVID-19 Patients Requiring Oxygen Supplementation							
Rationale: The severe acute respiratory syndrome coronavirus 2 (SARS-CoV-2) has resulted in the pandemic spread of coronavirus disease 2019 (COVID-19), which has a high rate of infection, has a high rate of hospitalization, has overwhelmed healthcare systems, and can be fatal. Ampion is the low molecular weight filtrate of human serum albumin with the in vitro ability to modulate inflammatory cytokine levels. Ampion has the potential to improve clinical outcomes for COVID-19 patients by reducing inflammatory cytokines correlated with the disease. This study aims to evaluate Ampion and clinical outcomes in patients with COVID-19 who require supplemental oxygen. The data from this study will inform decisions for the Ampion clinical development.							
Lead Investigators: [name], PhD, USA							
Number of Sites: Approximately 10 sites							
Indication: Adult COVID-19 patients on supplemental oxygen							
Number of Participants: Sample size is approximately 200 patients, randomized 1:1 for Ampion or control. An interim analysis will be conducted at 30 participants, randomized 1:1 for Ampion or control to allow for sample size re-estimation as needed.							
Treatment Groups: There are two planned treatment arms:							

Treatment Arm	Investigational Treatment	

Active	IV Ampion for 5-days	

Control	IV Placebo for 5-days	

		Treatment Arm	Investigational Treatment	Active	IV Ampion for 5-days	Control	IV Placebo for 5-days
Treatment Arm	Investigational Treatment						
Active	IV Ampion for 5-days						
Control	IV Placebo for 5-days						

Sponsor: Ampio Pharmaceuticals, Inc.	Investigational Product: Ampion™
Objectives and Endpoints:	
Objective	Endpoint
Primary	
Assess the effect of Ampion compared to placebo on prevention of need for mechanical ventilation or death	
Occurrence of mechanical ventilation or death by Day 28.
Secondary	

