4 SELECTION OF PARTICIPANTS

4.1 Number of Participants

The trial is designed to enroll up to approximately 200 patients across two treatment arms (active or control), with a 100 subjects per arm, randomized 1:1 using a random allocation sequence stratified by COVID-19 disease severity (severe or critical). An interim analysis of the data is planned after 30 subjects (n=15 subjects per arm) to evaluate the relative effect. At the interim analysis, the sample size may be re-estimated to determine the additional number of patients for adequate power up to the 200 subjects.

The number of participants is selected based on the effects observed for the primary endpoint. A study recently reported in Lancet Respiratory Medicine with 243 hospitalized patients receiving the placebo for COVID-19 found 22% did not achieve day 28 ventilation-free survival (Lancet Respir Med 2021; [https://doi.org/10.1016/S2213-2600\(21\)00494-X](https://doi.org/10.1016/S2213-2600(21)00494-X)). In the AP-014 study, a lower rate (8%) was observed for subjects receiving inhaled Ampion. Assuming the same proportions (8% for Ampion and 22% for control) by Day 28, with 100 subjects per group, a two-sided 5% significance level, and using a z-test with unpooled variances, then under binomial enumeration the power to detect this difference is about 81.3%.

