2.4 Sample Size

The trial is designed to enroll up to approximately 200 patients across two treatment arms (active or control), with 100 subjects per arm, randomized 1:1 using a random allocation sequence stratified by COVID-19 disease severity (severe or critical). An interim analysis of the data is planned after 30 subjects (approximately n=15 subjects per arm) to evaluate the relative effect. At the interim analysis, the sample size may be re-estimated to determine the additional number of patients required for adequate power to meet the chosen effect size for the primary endpoint.

The number of participants is selected based on the effects observed for the primary endpoint, prevention of need for mechanical ventilation or death prior to day 28. A study recently reported in Lancet Respiratory Medicine with 243 hospitalized patients receiving the placebo for COVID-19 found 22% did not achieve day 28 ventilation-free survival (Lancet Respir Med 2021; [https://doi.org/10.1016/S2213-2600\(21\)00494-X](https://doi.org/10.1016/S2213-2600(21)00494-X)). In the AP-014 study, a lower rate (8%) was observed for subjects receiving inhaled Ampion. Assuming the same proportions (8% for Ampion and 22% for control) by Day 28, with 100 subjects per group, a two-sided 5% significance level, and using a z-test with unpooled variances, then under binomial enumeration the power to detect this difference is about 81.3%.

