6. INTERIM ANALYSIS AND EARLY STOPPING GUIDELINES

6.1 Interim Analysis

This trial is designed to enroll up to approximately 200 subjects, randomized to active or control, following an equal allocation to treatment arms. An interim analysis of the data is planned after 30 subjects (approximately n=15 subjects per arm) to evaluate the relative treatment effect.

The interim analysis will be conducted on the primary and secondary endpoint data at an alpha level of 0.001 and thus the overall alpha level for the final test will be performed at approximately $\alpha=0.049$ instead of $\alpha=0.05$.

At the interim analysis, the sample size may be re-estimated to include additional subjects up to a total of 300 subjects to attain adequate power beyond the sample size of 200 originally calculated. This evaluation will be based on the methodology suggested by Gould et al. (Gould AL. Interim analyses for monitoring clinical trials that do not materially affect the type I error rate. Stat Med 1992; 11(1): 55-66) Let σ be the pooled rate of this study endpoint in the two arms, i.e. $\sigma=(p_{placebo}+p_{Ampion})/2$, where p is the incidence of the primary study endpoint in the respective groups. Let σ^* be the same value, but based on some assumed rates for these values from the beginning of the trial. Then the following sample size multiplier is determined:

$$f = [\sigma(1-\sigma)]/\sigma^*(1-\sigma^*)$$

If f is greater than 1, then the new sample size, n_1 , is determined as $f \times n$, where n is the original sample size (per group) of 100. If f is less than one, then the study will continue as originally envisioned.

The sponsor reserves the right to alter the final sample size if the assumptions of the rates of the primary endpoint are not satisfied at this interim analysis.

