6.2 Blinding Controls at Interim Analysis

The interim analysis will involve unblinded data. Only a small sequestered team will have access to the unblinded data and results. The data will not be transferred, or results viewed by any person involved in the day-to-day conduct of the clinical trial, including, but not limited to the blinded sponsor staff, Medical Monitor, and/or blinded CRO staff. These individuals will remain blinded to the results.

The unblinded team will be responsible for obtaining the required material for the analysis from the study's unblinded data manager (DM) for the clinical trial. The unblinded team will present

Statistical Analysis Plan (SAP) for Clinical Study AP-017

the results of the interim analysis to the sponsor in a blinded fashion (e.g., a simple recommendation to increase sample size or keep sample size as defined in the SAP without presenting the details surrounding the raw data, results, or efficacy conclusions).

All individuals on the sequestered team who are unblinded will be documented and archived by the sponsor.

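### For the same 30-patient interim, the protocol re-estimates up to 200 patients and the SAP up to 300 by a rule that can only increase; the final alpha also differs (0.047 against about 0.049)

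*Protocol*

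**What the plan says.** Both documents plan one interim analysis after 30 patients, about 15 per arm, at alpha 0.001.

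**Maximum size**
- Protocol 9.2.3 re-estimates "to attain adequate power up to a 200 total subjects". Protocol 4.1 agrees: the size may be "re-estimated to determine the additional number of patients for adequate power up to the 200 subjects".
- SAP 6.1 sets a higher ceiling: "re-estimated to include additional subjects up to a total of 300 subjects to attain adequate power beyond the sample size of 200 originally calculated". The new size is f times 100 per group when f exceeds 1. Otherwise: "If f is less than one, then the study will continue as originally envisioned".
- The protocol synopsis ("to allow for sample size re-estimation as needed") and SAP 2.4 ("additional number of patients required for adequate power to meet the chosen effect size for the primary endpoint") give no cap.
- Both documents also let the sponsor alter the final size if planning rates are not met at the interim, with no limit. The protocol ties this to death rates, the SAP to primary-endpoint rates.

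**Final alpha**
- Protocol 9.2.3 sets the interim test "at an alpha level of 0.001 and thus the overall alpha level for the final test will be performed at $\alpha=0.047". SAP 6.1 gives approximately 0.049 after the same look.

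SAP section 9 lists two departures from the protocol, the amended primary endpoint and the ordering of the secondary endpoints. It mentions neither the 300 nor the 0.049.

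**The concern.** The protocol's ceiling is already the planned size, and the SAP rule never goes below it. The SAP rule therefore agrees with the protocol only when it does nothing.

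The conflict reaches the people who must act. Under SAP 6.2 the unblinded team gives the sponsor "a simple recommendation to increase sample size or keep sample size as defined in the SAP". It works from the SAP, so it could properly recommend 252 or 300 patients while the protocol says up to 200. Neither document says which governs. Settling this after someone has seen unblinded data would invite the question whether the results guided the choice.

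The alpha difference is smaller. However, a primary p-value between 0.047 and 0.049 would succeed under one document and fail under the other.

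**Working it through.** **1. The plan's own power figure.** Inputs from protocol 4.1 and 9.1 and SAP 2.4: 8% against 22%, 100 per group, two-sided 5%, z-test with unpooled variances. Enumerating both binomial distributions gives 81.28%, which matches the stated 81.3%.

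**2. What the SAP rule does.** SAP 6.1 sets f = σ(1−σ) / [σ*(1−σ*)], where σ is the mean of the two arms' interim rates and σ* the same quantity from the planning rates. The SAP gives no value for σ*. I take (0.08 + 0.22)/2 = 0.15, so the denominator is 0.15 × 0.85 = 0.1275. With 15 per arm, σ = events/30. I round 100f up and cap it at 300/2 = 150 per group.

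| Events in 30 | σ | σ(1−σ) | f | Per group | Total |
|---|---|---|---|---|---|
| 4 | 0.133 | 0.1156 | 0.906 | 100 | 200 |
| 5 | 0.167 | 0.1389 | 1.089 | 109 | 218 |
| 6 | 0.200 | 0.1600 | 1.255 | 126 | 252 |
| 7 | 0.233 | 0.1789 | 1.403 | 141 | 282 |
| 8 | 0.267 | 0.1956 | 1.534 | 154, capped at 150 | 300 |

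Fewer than 4 events also leave 200. The cap applies from 8 to 22 events. Above 22, σ(1−σ) falls again, but such counts do not matter in practice.

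**3. How often it acts.** The event count is Bin(15, p_Ampion) + Bin(15, p_control).

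| True rates | Rule raises size | Total 300 | Mean total |
|---|---|---|---|
| 8% and 22% (as planned) | 47.7% | 6.6% | 224 |
| 22% in both arms | 82.1% | 33.3% | 259 |

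At the planned rates the total is 252 or more in 28.7% of interims, and the mean is 250 when the rule acts.

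**4. Final alpha after a 0.001 look.**
- Subtraction: 0.05 − 0.001 = 0.049.
- Allowing for correlation between the looks (bivariate normal, correlation √(30/200) or √(30/300)), the largest final level that keeps 0.05 overall is 0.0493 or 0.0492.
- The protocol's pair adds to 0.001 + 0.047 = 0.048, so it spends less than 0.05. By subtraction, 0.047 would match an interim look at 0.003.

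**5. What the alpha gap costs.** At 100 per group, 8% against 22%, by enumeration:

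| Test | Power at 0.049 | Power at 0.047 | Chance p lies between |
|---|---|---|---|
| Pearson chi-square | 81.2% | 80.2% | 1.0% |
| Fisher's exact | 74.9% | 74.2% | 0.7% |
| Unpooled z | 81.3% | 81.2% | 0.1% |

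For example, 10 against 20 events gives Pearson p = 0.0477: significant at 0.049, not at 0.047. For the same table the two levels agree under unpooled z (0.0455) and Fisher (0.073).

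**6. What the SAP rule gains.** At the planning rates, with Pearson at 0.049 and the interim patients included, power is 84.1% under the rule against 81.2% at a fixed 100 per group.

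**The case against.** The best defence is that 200 was never a hard ceiling. Both documents call it approximate. Protocol 9.2.3 itself reserves a right to change the size if the rate assumptions fail, and f > 1 is a check of the pooled rate, so the SAP rule could be read as spelling out that right. Protocol 9.1 also leaves analysis details to the SAP.

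Part of this stands: an increase is not plainly forbidden, and an approximate 200 might absorb 218. It does not absorb 252 to 300. The reserved right has no limit and no rule, and in the protocol it refers to deaths alone, although 8% and 22% are rates of ventilation or death. Leaving analysis details to the SAP does not hand over maximum enrolment, and protocol 10.3 requires a written amendment for any change to the protocol.

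On alpha, the objection is that 0.047 cannot inflate the error spent over the two looks and that power barely moves. That is right, and it makes this part minor. The figure still does not follow from the 0.001 from which the protocol derives it.

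**Conclusion.** The concern holds. The two documents give different maximum sizes, 200 and 300, for the same interim, and different final significance levels. Neither difference is declared as a change from the protocol.

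The size conflict is the substantive part. The SAP rule would exceed 200 in about half of interims if planning is right and in about four-fifths if both arms run at 22%. These figures assume σ* = 0.15, exactly 15 patients per arm and rounding up. The contradiction itself needs none of these assumptions.

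The alpha difference is a minor inconsistency in the conservative direction, worth at most about one point of power. Both should be corrected before the interim.

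**What to change.** Before any interim data are unblinded:

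1. **State one maximum size** in the protocol synopsis, protocol 4.1 and 9.2.3, and SAP 2.4 and 6.1.
   - *Hold 200:* delete the increase rule from SAP 6.1 and align SAP 1, 2.4 and 6.2, which refer to additional patients or a possible increase. The protocol's re-estimation text then has no function, since 200 is already the planned size, and should be removed or explained. This needs no patients and gives up about 3 points of power at the planning rates (81.2% against 84.1%).
   - *Allow 300:* amend the protocol, put the rule in it and write σ* = 0.15 in SAP 6.1. This costs up to 100 more patients, 24 on average if planning is right.
2. **Bound the sponsor's right** by that maximum and the stated rule, and refer to primary-endpoint rates in both documents.
3. **State one final alpha.** 0.049 is what a 0.001 look leaves and changes only the value in protocol 9.2.3. 0.047 is acceptable if described as deliberately conservative; that changes SAP 6.1 and the protocol's explanation. Neither needs patients.
4. **Restate power** at the chosen alpha for the test to be used (at 0.049: Pearson 81.2%, Fisher 74.9%).
5. **List in SAP section 9** any departure from the protocol that remains.

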9.3 Data presentation

9.3.1.1 Demographic and Baseline Characteristics:

Demographic (e.g., age, sex, race, ethnicity) and baseline characteristics (e.g., weight, height, comorbidities) summarized using descriptive statistics, overall and by treatment group for the ITT and safety analysis population.

9.3.1.2 Medical History and Physical Examination:

The number and percent of participants with past and current medical disorders at the time of randomization will be presented overall and by treatment group for the ITT and safety analysis population.

9.3.1.3 Concomitant Medications or Treatments:

The number and percent of subjects receiving concomitant medications or therapies prior to and during the study and at the final visit will be tabulated and presented overall and by treatment group for the ITT analysis population.

Concomitant medications/treatments will be summarized using descriptive statistics and will be presented by type of drug (WHO DRUG classification) overall and by treatment group for the safety and ITT analysis populations. There should be no significant differences in the use of concomitant treatments between groups. All concomitant therapies will be recorded to be able to compare any inadvertent imbalances between the groups.

9.3.1.4 Safety Data:

Safety data will be presented by treatment arm. Safety data will be evaluated by changes in vital sign measurements, laboratory assessments, and the frequency and severity of AEs. Concomitant medication will be recorded for safety. AEs will be collected from baseline to Day 60. The severity of AEs (mild, moderate, severe), relatedness (related, possibly related, unrelated) along with the duration, action taken, and outcome (e.g., study withdrawal) will also be recorded.

All data collected under this study protocol will be included in the assessment of patient safety. Missing or incomplete AE data will assume greatest relationship to study drug and/or severity.

Remaining safety data will be collected from enrollment through index hospitalization until hospital discharge (or in-hospital death). Safety data will be tabulated and presented overall and by treatment group for the safety analysis population.

9.3.1.5 Efficacy Data:

The efficacy of treatment on the clinical course and outcome of COVID-19 will be evaluated by treatment arm. Summaries will be performed by severity (severe or critical), individually, and combined.

Unless otherwise specified, continuous variables will be summarized with the number of non-missing observations, mean, standard deviation, median, minimum, maximum, and 95% confidence intervals displayed. Categorical data will be summarized as counts, percentages, and 95% confidence intervals.

9.4 Study Endpoints

9.4.1 Primary Endpoint

The primary endpoint assesses the effect of Ampion compared to placebo on the prevention of need for mechanical ventilation or death. This is measured as the occurrence of mechanical ventilation or death by Day 28.

Let π_A and π_S represent the rate of this outcome for Ampion and control during the first 28 days after randomization. Then it is desired to demonstrate that the mechanical ventilation and death rate for Ampion is different than the corresponding rate for the control. Formally, this is presented as:

$$H_0: \pi_A = \pi_S \text{ versus } H_A: \pi_A \neq \pi_S$$

This will be tested utilizing the appropriate chi-square test or Fisher's exact test utilizing PROC FREQ with the EXACT option, if necessary.

